**Table 1. Probability of observing at least 1 SAE for samples sizes of 10 and 40 with different true SAE rates**

True rate of severe adverse events	Probability of observing at least one participant with SAE (Halting rule 1)	
	N=10	N=40
.001	0.01	0.04
0.01	0.10	0.33
0.02	0.18	0.55
0.03	0.26	0.70
0.04	0.34	0.80
0.05	0.40	0.87
0.06	0.46	0.92
0.07	0.52	0.95
0.08	0.57	0.96
0.09	0.61	0.98
0.1	0.65	0.99
0.11	0.69	0.99
0.12	.72	0.99
0.13	0.75	0.99
.14	0.78	0.99
0.15	0.80	0.99

**Table 2. Probability of observing at least 2 SAE’s for samples sizes of 10 and 40 with different true SAE rates**

True rate of severe adverse events	Probability of observing at least 2AE’s (halting rule 2)	
	N=10	N=40
.01	<.001	.06
.08	.19	.84
.27	.80	>.99

### 14.3 Analysis Plan

T-tests will be used to compare immunogenicity endpoint measurements for the primary endpoint and other continuous endpoints between each treatment group and the placebo group. For binary endpoints Fishers exact test will be used. AEs will be tabulated by treatment arm.

The fold increase in cellular and humoral responses to AGS-v PLUS from day 1 to days 43 and 50, and from day 43 to day 50 will be calculated for each participant. The mean fold increases on each active group will be compared to the mean fold increases in the placebo group. The geometric mean antibody titers and geometric mean cytokine concentrations to AGS-v PLUS on days 1, 43, and 50 will be calculated and compared between the different treatment groups.

The fold increase in cellular responses to mosquito saliva from day 1 to days 43 and 50, and from day 43 to day 50 will be calculated for each participant. The mean fold increases on each active group will be compared to the mean fold increases in the placebo group. The geometric mean cytokine concentrations to mosquito saliva on days 1, 43 and 50 will be calculated for each treatment group and compared to placebo.

For the mosquito analysis, the following parameters will be compared on the active groups versus placebo for each mosquito (*Aedes aegypti* and *Aedes albopictus*):

- mean number of days mosquitoes survive after feeding on vaccinated participants
- mean number of eggs laid
- mean number of mosquitoes emerging from the laid eggs

For the visual assessment of the mosquito bite the following parameters will be calculated for each group and active groups will be compared to placebo at three different time points: day 43 (30 min post feeding), day 45 and day 50:

- mean number of visible bites
- mean redness measured across the widest part (mm)
- mean swelling measured using the ball point pen method (mm^2). Ball point pen measurement of induration uses the pen to slide on top of the skin so it halts at the edge of true induration (versus redness)

From the biopsies taken on day 45, the following comparisons will be made:

-gene expression: the level of expression of inflammatory cytokines at the bite site compared to normal skin (control) will be calculated for each participant for each mosquito bite. The mean will be calculated in each group and compared to placebo.

The viability/infectivity of Zika virus after culture with PBMCs and serum from vaccinated participants will be assessed by infecting Vero cells with the cell supernatant followed by measuring viability of Vero cells using MTT assay. The higher the infectivity of the Zika virus the lower the MTT value will be for Vero cells. The fold changes from day 0 to day 43 will be measured for each participant and the mean calculated for each group and compared to placebo.

For randomization, the first 10 participants will be randomized into 5 arms with 2 in each arm. An interim safety analysis after the first group of 10 participants have received the first immunization and completed the Day 8 phone call will be done by the DSMB by teleconference. Recruitment activities will continue but vaccination of new participants will be halted until the DSMB review has been completed. Once the interim safety analysis is done on the initial enrolment, an additional set of 40 participants will be enrolled and randomized using a permuted block randomization with a block size of 10.

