## 3.2 Study Endpoints

### Primary:

1. Incidence and severity of treatment emergent adverse events (AEs) and serious adverse events (SAEs).
2. Geometric mean titer and fold increase in serum AGS-v PLUS specific immunoglobulin G (IgG), immunoglobulin M (IgM) and immunoglobulin E (IgE) titers from day 1 to day 43.
3. Geometric mean concentration and fold increase in Th1 and Th2 cytokine responses (from day 1 to day 43) after *in vitro* exposure of PBMCs with AGS-v PLUS antigens.

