- Phase 1 AGS-v 001: Safety issues had been mild in severity. The vaccinations were well tolerated. In the unadjuvanted AGS-v group the most common AEs were Grade 1 or 2 injection site pain, fatigue, and headache (37.5%, 31.3%, 31.3% of participants respectively). Some participants also experienced Grade 1 or 2 systemic reactions of myalgia/feverishness/chills/diaphoresis (6.1-18.8% of participants). The adjuvanted AGS-v group experienced a higher level of related AEs, with the most common being injection site pain, swelling, erythema, and pruritis (52.9%, 47.1%, 41.2%, and 41.2% respectively). They also experienced some systemic grade 1 and 2 AEs such as fatigue (41.2%) and feverishness (35.3%), as well as myalgia, chills and diaphoresis (5.9-29.4%). The placebo group experienced fewer AEs with only injection site pain and erythema in 25% and 6.3% respectively. They experienced a smaller amount of systemic AEs as well ranging from 6.3% to 12.5% for headache, fever, chills, fatigue, and myalgia. The most common AEs on Mosquito Feeding Day were Grade 1 erythema (93.8%) and Grade 1 local swelling (93.8%).
- Phase 1 FLU-v-001: no deaths occurred and only one SAE was reported with this being considered unrelated to FLU-v (appendicitis). There was no apparent increase in adverse events (AEs) with a change in dose from the 250 µg or 500 µg (500 µg of FLU-v is the equivalent of 825 µg of AGS-v as both contain 50 nmol of each peptide and a total of four peptides), but an approximate two-fold increase in AEs was seen in the adjuvant versus non-adjuvant groups. This latter point is likely responsible for the largely local administration site reaction AEs, and the forearm site and 1 ml volume is suspected to be the cause rather than the adjuvant itself. In conclusion, no safety or tolerability concerns were identified.
- Phase 1b FLU-v-002: all 32 participants reported AEs: 32 mild, 10 moderate and one severe (a pre-syncopal episode in the placebo group). There were no deaths or SAEs. The most frequently reported AEs were related to the injection site reactogenicity and are consistent with those already documented with use of the adjuvant. There were no other clinically significant changes in the other safety parameters (complete physical examination, clinical chemistry, hematology and urinalysis, vital signs including oral temperature, electrocardiogram [ECG]).

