Since this is a Phase 1b study we are looking for activity of the vaccine that would indicate the vaccines should be studied further. Since we do not wish to expose more participants than necessary to an experimental vaccine but we also don't wish to miss an active vaccine we will design the study to have 85% power with a one sided type I error rate of 0.1. We will also not adjust for the multiple comparisons (4 active arms being compared to placebo).

With 10 participants per arm, there will be at least 85% power to detect a true difference in the primary immunogenicity endpoint of 0.95 standard deviations using a one-sided t-test with significance level of 0.1(R version 3.4.1).

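### If binary endpoints are tested against placebo at 10 v 10, Fisher's exact test is very conservative; Boschloo's exact test keeps the same nominal level and is never less powerful

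*Combined protocol and SAP*

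**What the plan says.** Section 14.3 (Analysis Plan) assigns t-tests to continuous endpoints and then says: "For binary endpoints Fishers exact test will be used. AEs will be tabulated by treatment arm". No significance level, sidedness or list of binary endpoints is given there.

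In section 3.2 the one primary endpoint that is naturally binary per participant is "Incidence and severity of treatment emergent adverse events (AEs) and serious adverse events (SAEs"). The other endpoints are titres, concentrations, survival and egg counts, bite sizes, expression levels and assay values. The first primary objective (section 2.1) is safety and tolerability against saline placebo, and section 3.1 allocates 10 participants to each of five arms.

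The only error rate in the plan is in section 14.2: "we will design the study to have 85% power with a one sided type I error rate of 0.1". It is set there in a discussion of vaccine activity and applied to a "true difference in the primary immunogenicity endpoint of 0.95 standard deviations using a one-sided t-test with significance level of 0.1". The same section adds: "We will also not adjust for the multiple comparisons (4 active arms being compared to placebo").

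**The concern.** With 10 participants per arm, Fisher's test conditions on the total number of events, so only a few p-values are attainable. The test then runs well below its nominal level at every underlying rate. It remains valid, but it gives up power that another exact test would keep at the same nominal level.

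Each comparison with placebo rests on 20 people. If local or systemic reactions are compared formally, differences of the size seen with the related vaccine AGS-v would often not be flagged, although the same data could show them under a test that is also exact.

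**Working it through.** **The plan's own figures.** The plan states no power for a binary comparison with placebo. Its safety figures are chances of seeing events, and they reproduce: 1 − 0.85^10 = 0.803 (stated 80%) and 1 − 0.93^40 = 0.945 (stated 95%). They do not bear on the choice of test.

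**Inputs.** 10 per arm (section 3.1). Rates from the AGS-v 001 summary in section 8.2: erythema 41.2% adjuvanted v 6.3% placebo; injection-site pain 52.9% v 25%. Section 8.2 says of placebo: "The placebo group experienced fewer AEs with only injection site pain and erythema in 25% and 6.3% respectively". Since 14.3 gives no level, three are shown.

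**Step 1: p-values.** With a events in the active arm and c on placebo, the one-sided Fisher p is the hypergeometric tail given a + c.
- 3/10 v 0/10: C(10,3)/C(20,3) = 120/1140 = 0.105.
- 4/10 v 1/10: [C(10,4)·C(10,1) + C(10,5)]/C(20,5) = 2352/15504 = 0.152.

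Boschloo's test uses Fisher's p as its statistic. Its p-value is the largest probability, over a common event rate, of a Fisher p at least as small. For the same two tables it gives 0.058 and 0.076.

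**Step 2: rejection regions at one-sided 0.10.** Smallest active count that rejects:

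| Placebo events | 0 | 1 | 2 | 3 | 4 | 5 | 6 | 7 |
|---|---|---|---|---|---|---|---|---|
| Fisher | 4 | 5 | 6 | 7 | 8 | 9 | 10 | none |
| Boschloo | 3 | 4 | 5 | 7 | 8 | 8 | 9 | 10 |

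Boschloo's region contains Fisher's, so it cannot be less powerful.

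**Step 3: true size.** All 11 × 11 = 121 outcomes were enumerated and the rejection probability maximised over a common rate.

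| Nominal level | Fisher maximum | Boschloo maximum |
|---|---|---|
| One-sided 0.10 | 5.8% | 9.9% |
| One-sided 0.05 | 2.1% | 4.5% |
| Two-sided 0.05 | 1.3% | 4.2% |

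**Step 4: power.** Power is the sum over c of P(C = c) × P(A ≥ critical value for c). For erythema at one-sided 0.10, the weights P(C = c) for c = 0, 1, 2, 3 are 0.5217, 0.3507, 0.1061 and 0.0190.
- Fisher: 0.5217×0.6473 + 0.3507×0.3973 + 0.1061×0.1870 + 0.0190×0.0642 = 0.498.
- Boschloo: 0.5217×0.8513 + 0.3507×0.6473 + 0.1061×0.3973 + 0.0190×0.0642 = 0.715.
- Terms beyond c = 3 are negligible.

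| Comparison | One-sided 0.10 | One-sided 0.05 | Two-sided 0.05 |
|---|---|---|---|
| Erythema, 41.2% v 6.3% | 50% → 72% | 41% → 50% | 23% → 41% |
| Pain, 52.9% v 25% | 37% → 49% | 22% → 34% | 11% → 22% |

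**Step 5: where the gain is small.** At one-sided 0.10:
- Rare events at an illustrative 5% v 1%: 0.1% → 1.0%.
- A very large difference, 93% v 18.8% (related TEAEs in the FLU-v003 summary, section 8.2): 99.1% → 99.6%.
- An assumed 70% v 30%: 60.8% → 66.5%.

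**The case against.** A reader might infer that the plan sets a 10% one-sided error for AE comparisons and that Fisher's test wastes nearly half of it. The documents do not support that. Section 14.2 sets the level so as not to miss an active vaccine and applies it to the immunogenicity t-test, and 14.3 promises only a tabulation of AEs. Any loss of power is therefore conditional on tests being run, and the 10% column is an assumption.

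Safety decisions also do not rest on a p-value. Section 14.2 sizes safety on the chance of seeing one or two events, section 12.9 halts on counts of related events, and the DSMB reviews the data. A table showing 3 v 0 reads the same whether p is 0.105 or 0.058. This stands, and it limits the consequence.

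Nor is the gain free or uniform. At one-sided 0.10 the worst-case false-positive rate per comparison rises from 5.8% to 9.9%. Section 7.2 names 13 local and general symptoms; across four active arms that could mean 13 × 4 = 52 unadjusted tests. This also stands, and is why the comparisons should be labelled descriptive.

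Finally, Fisher's test is valid, and using it at this sample size is not an error. But the alternative is also exact, is never less powerful, and costs one sentence.

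**Conclusion.** The point holds as a cheap improvement, not as an error in the plan. Section 14.3 names a binary test without level, sidedness or endpoint. If that test is used for 10 v 10 comparisons with placebo, it runs well below nominal at each of the three levels examined. At the AGS-v 001 rates, Boschloo's test adds about 22 points of power for erythema and 11 for pain at one-sided 0.10, 9 and 12 at one-sided 0.05, and 18 and 11 at two-sided 0.05. It adds almost nothing for rare SAEs, and at one-sided 0.10 almost nothing for very large differences.

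These figures assume that active-versus-placebo tests are run, that all 10 participants per arm contribute, and that AGS-v PLUS reaction rates resemble those of AGS-v. They do not show that the planned safety assessment would fail.

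**What to change.** In section 14.3, replace the Fisher sentence with text such as: *Any comparison of a binary endpoint between an active group and placebo will use Boschloo's exact unconditional test at [level, sidedness], with an exact unconditional confidence interval for the risk difference. Comparisons of AE incidence are descriptive and unadjusted for multiplicity.* Keep the tabulation of AEs by arm. The sponsor should fill in the level and sidedness explicitly; the immunogenicity level should not carry over by default.

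Cost: a short edit and a standard software routine, with no new data or participants. Downsides: a less familiar test, and more differences flagged by chance within the nominal level (worst case 9.9% instead of 5.8% per comparison at one-sided 0.10). The halting rules are unaffected.

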### Secondary:

1. Geometric mean titer and fold increase in AGS-v PLUS specific IgG, IgM and IgE titers seven days after mosquito feeding (day 50) compared to day 1 and 43.
2. Geometric mean concentration and fold increase in AGS-v PLUS specific Th1 and Th2 cytokine responses in the supernatants of PBMCs (day 50 compared to days 1 and 43) after *in vitro* exposure with AGS-v plus.
3. Survival and fecundity in *Aedes aegypti* and *Aedes albopictus* female mosquitoes after feeding on vaccinated participants.

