#### 7.1.1 Laboratory Testing of Collected Samples for Primary and Secondary Endpoints

- AGS-v PLUS specific IgG, IgM and IgE assay will be performed using enzyme-linked immunosorbent assay (ELISA). The time points assayed will be day 1, day 43 and day 50.
- Th1 and Th2 response assays: PBMCs collected from participants will be incubated with AGS-v PLUS and saliva from *Aedes aegypti*, *Aedes albopictus* and *Anopheles gambiae* and measurements of Th1 (Interferon-gamma) and Th2 (Interleukin-4) cytokines will be performed using ELISA. The time points assayed will be day 1, day 43 and day 50.
- Biopsies taken on day 45 will be used to assess expression of inflammatory markers.
- Feeding on human volunteers: 24 hour after emergence from pupae, male and female *Aedes aegypti* and *Aedes albopictus* mosquitoes will be allowed to mate for 24-48 hours. After this period, female mosquitoes will be separated from males. These mosquitoes would have only been sugar-fed up until now. Female mosquitoes will be placed in a secured Plexiglass feeding device and allowed to feed on the volunteer's arms on Day 43 (approximately 21 days after they have completed the vaccination schedule). Each participant from each arm will be exposed to the bites of *Aedes aegypti* on the right arm and *Aedes albopictus* on the left arm. Mosquitoes that had a blood meal will then be removed and followed up to assess any changes to their life cycle, i.e., life-span, number of eggs laid, number of fertile eggs, number of surviving larvae etc. The mosquito colony used in this study will not be fed on human blood before exposure to participants, but on non-mammalian blood to minimize the presence of blood borne pathogens.
- Zika virus killing, *in vitro* toxicity assay:
  - Blood samples will be obtained from all volunteers 21 days after vaccination is completed (day 43 pre-feeding). PBMCs+sera containing immune cells and antibodies generated against AGS-v PLUS will be tested for their ability to kill or inactivate Zika virus coated with salivary gland proteins from *Aedes aegypti* and *Aedes albopictus*. Viability of the virus will be tested by infecting Vero cells with the PBMC/virus supernatants. Infectivity of the Zika virus will be assessed by measuring the viability of the Vero cells using MTT assay.
  - Zika virus will be obtained from commercial suppliers and will be propagated *in vitro*.

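### Section 14.3 never uses day 1 as a covariate and leaves the scale of the fold-increase t-test unstated; log-scale ANCOVA is inexpensive protection, not a guaranteed gain

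*Combined protocol and SAP*

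**What the plan says.** Section 3.2 makes two summaries primary for antibodies, "Geometric mean titer and fold increase in serum AGS-v PLUS specific immunoglobulin G (IgG" and the other isotypes, from day 1 to day 43. It does the same for cytokines with concentrations. Section 7.1.1 has antibodies and cytokines measured at baseline and twice later: "The time points assayed will be day 1, day 43 and day 50".

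Section 14.3 sets the tests: "T-tests will be used to compare immunogenicity endpoint measurements for the primary endpoint and other continuous endpoints between each treatment group and the placebo group". Folds are taken "from day 1 to days 43 and 50, and from day 43 to day 50 will be calculated for each participant", and then "The mean fold increases on each active group will be compared to the mean fold increases in the placebo group". Beside this, "The geometric mean antibody titers and geometric mean cytokine concentrations to AGS-v PLUS on days 1, 43, and 50 will be calculated and compared" between groups. Saliva-stimulated cytokines are handled in the same way. No baseline covariate is named anywhere.

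Section 14.2 bases the immunogenicity sample size on 10 per arm, a one-sided t-test at 0.1 and a difference of 0.95 SD, without saying which measure or scale that SD belongs to.

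**The concern.** Two gaps sit side by side.

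- **Day 1 as covariate.** In the post-vaccination comparisons day 1 is either divided out in full (fold) or ignored (geometric means at day 43 or day 50). Dividing it out suits a high rho, and ignoring it suits a low one. The documents do not give rho, so the sponsor cannot know which planned test is the weak one. ANCOVA estimates the weight from the data.
- **Scale of the fold test.** Section 14.3 writes geometric mean for titers and concentrations but plain mean for folds. One analyst could test raw folds and another log folds, and they would report different p-values for a primary endpoint.

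At stake is the sensitivity of an activity screen inside a Phase 1 safety study, and its reproducibility. Participant protection is not affected.

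**Working it through.** **Inputs from the documents.** 10 per arm, one-sided 0.10, difference 0.95 SD (Section 14.2). Pairwise t-tests against placebo (Section 14.3).

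**Assumptions, because the documents give none.** Lognormal values, rho from 0 to 0.7, equal log SDs on both days (log10 SD 0.5 where raw fold is simulated).

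**The plan's own figure.** Noncentral t, 18 df, noncentrality 0.95/√(2/10) = 2.12, gives 78.6%, against at least 85% in Section 14.2. That discrepancy is a separate matter and is not used as support here. The 78.6% appears below only because it is the power of the day 43 t-test.

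**Formulas for a uniform shift of 0.95 SD of log day 43.**

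- Log day 43: noncentrality 0.95/√0.2, 18 df.
- Log fold: the SD of the change is √(2(1−rho)), so the noncentrality is 0.95/√(2(1−rho))/√0.2, 18 df.
- ANCOVA: the residual SD is √(1−rho²), with a factor 1 + 1/(2×10−4) = 1.0625 for chance baseline imbalance. The noncentrality is 0.95/√(1−rho²)/√(0.2×1.0625), 17 df. At rho 0.5 this is 1.097/0.461 = 2.38, which gives 85.1%.

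| rho | ANCOVA | log day 43 | log fold | raw fold (simulated) |
|---|---|---|---|---|
| 0 | 76.7% | 78.6% | 57.4% | 43% |
| 0.3 | 79.5% | 78.6% | 68.2% | 56% |
| 0.5 | 85.1% | 78.6% | 78.6% | 69% |
| 0.7 | 93.7% | 78.6% | 91.9% | 86% |

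Simulation agrees with the formulas. ANCOVA overtakes log day 43 at rho of about 0.25. Its largest shortfall against the better log-scale test is 78.6 − 76.7 = 1.9 points. Log fold trails log day 43 by 21 points at rho 0, and log day 43 trails ANCOVA by 15 at rho 0.7. With no effect and equal spread, all four tests reject between about 9.3% and 10.2%.

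**If 0.95 SD means the SD of log fold** (rho 0/0.3/0.5/0.7): ANCOVA 94/89/85/82%, log fold 79% throughout, log day 43 95/88/79/63%. The pattern is the same, with the weak test exchanged.

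**Where the gain shrinks or reverses.**

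- *Day 1 barely varies* (SD a quarter of that at day 43; rho 0/0.3/0.5): log fold 76.8/81.3/84.6% against ANCOVA 76.7/79.5/85.1%.
- *Assay floor* (rho 0.3/0.5/0.7): ANCOVA minus log day 43 is +1/+6/+15 points with no day 1 values at the floor, 0/+4/+13 with half there, and −1/+2/+9 with 75% there. In the last case ANCOVA can be about 3 points below the better log-scale test.
- *Partial responders.* Section 1 reports antibody responses in 60% and cellular responses in about 50% for HIV-v. Take a 10-fold rise in 50% or 60% of vaccinees, log10 SD 0.3/0.4/0.5 and rho 0/0.3/0.5/0.7: 2×3×4 = 24 settings. Raw fold has more power than ANCOVA in 12 of 24, including 10 of the 12 at rho 0.5-0.7. With 50% responders, SD 0.4 and rho 0.7 it is 92.6% against 85.1%. At the other extreme ANCOVA leads raw fold by 22 points. ANCOVA minus log day 43 runs from about −2 to +10.

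**Day 43 to day 50.** Day 43 falls "approximately 21 days after they have completed the vaccination schedule", so it is a post-vaccination value. Suppose vaccinees sit 0.95 SD above placebo on both days, with no difference in change. At rho 0.5/0.7/0.9 the log-fold t-test rejects 10% throughout, while ANCOVA adjusting for day 43 rejects about 41/30/20%. Adjustment there asks a different question.

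**The case against.** The strongest case against is that this is a preference between valid methods. Fold increase is a named endpoint, a geometric-mean comparison is already planned, and the sample size is built on a t-test. In the one scenario tied to a figure in the documents, partial response, ANCOVA rarely beats both planned comparisons by a useful margin. At low rho the day 43 test already matches it, and at high rho raw fold usually wins. Section 3.2 can also be read as applying geometric mean to the fold as well, which would settle the scale. Most of this stands. It removes any claim of a general efficiency gain, but not the case for protection among the log-scale tests or the need to name a scale.

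A reader might infer four stronger points that the documents do not support:

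- *The t-tests are invalid.* They hold about 10% in the equal-spread null settings tested.
- *Day 1 serves only as the fold denominator.* Section 14.3 also compares day 1 geometric means between groups.
- *ANCOVA always has more power.* It does not at low rho, with baselines that barely vary or sit at the floor, or against raw fold with partial response.
- *ANCOVA restores the 85% in Section 14.2.* It reaches 85% only if rho is about 0.5 or more under the first reading of 0.95 SD, and rho is unknown.

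**Conclusion.** The point holds as a low-cost improvement. Day 1 is collected and never used as a covariate, and the scale of the fold test is not stated. With equal log SDs, a uniform shift and no assay floor, ANCOVA gives up at most about 2 points to the better log-scale test, while choosing the wrong one of those two can cost 15 points or more. The size depends on rho, the SDs, the share of values at the floor and the share of responders, none of which the documents give for this vaccine. No conclusion of the trial becomes unsound if the plan stays as it is.

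**What to change.** For AGS-v PLUS antibodies and cytokines and for saliva-stimulated cytokines, write in the analysis plan before unblinding:

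> Log10 day 43 values (and log10 day 50 values for the day 50 versus day 1 comparison) will be compared between each active arm and placebo by ANCOVA with log10 day 1 as covariate, reported as a geometric mean ratio with confidence interval; this ratio is also the baseline-adjusted ratio of geometric mean fold increases. If day 1 values do not vary (all at the assay floor), the unadjusted t-test on log10 values will be used. The day 43 to day 50 change will be compared by t-test on log10(day 50/day 43). Geometric mean fold rises and individual fold rises will be shown.

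The cost is SAP wording and one residual degree of freedom (18 to 17), with no new data. The price in power is up to about 2 points against log day 43 when rho is below about 0.25, and up to about 8 points against a raw-fold t-test if only about half of vaccinees respond. Showing individual fold rises keeps such responders visible.
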